### 4.2 Inclusion Criteria

- 1. Male or female, aged 18-70 years.
- 2. A reliable history consistent with moderate to severe rhinoconjunctivitis (sneezing, rhinorrhoea, itchy nose, nasal blockage and/or itchy eyes, red eyes, watering eyes and/or itchy ear/palate) on exposure to HDM for at least 1 year and which has required symptomatic treatment on at least one occasion during the last year.
- 3. Mean TRSS ≥10 from 4 nasal and 4 non-nasal symptoms over a consecutive 7 day period before the Screening Visit 1B/C.
- 4. Either Der p or Der f specific IgE  $\geq 0.35$  kU/L measured by ImmunoCAP®.

VERSION FINAL 4.0 CONFIDENTIAL PAGE 25 OF 92

- 5. Positive skin prick test (preferably using the ALK-Abello Allergen Extract test) to either Der p or Der f with a wheal diameter at least 5 mm (average of longest and orthogonal) larger than that produced by the negative control. The negative control must be <2 mm for the test to be valid.
- 6. Provide written informed consent.
- 7. Willing and able to comply with the study requirements.
- 8. If female of childbearing potential (FOCBP), must practice a form of contraception with a failure rate of <1% when used correctly and produce a negative urine pregnancy test at the Screening Visit 1B/C.

### Additional Inclusion Criteria at End of BAE

- 9. Mean TRSS ≥12 from 4 nasal and 4 non-nasal symptoms during the BAE period (3-week period before randomisation).
- 10. Completed the eDiary during the BAE on at least 16 days (>75% of occasions).

### 4.3 Exclusion Criteria

- 1. Diagnosis of asthma requiring GINA Step 3 or higher treatment.
- 2. If asthmatic, experienced a deterioration of asthma that resulted in emergency treatment or hospitalisation in the 12 months before randomisation, or experienced a life-threatening asthma attack (e.g. one requiring intubation and mechanical ventilation) at any time in the past.
- 3. Used any oral or parenteral corticosteroids at any time within 1 month prior to Screening Visit 1B/C.
- 4. Asthma requiring high-dose inhaled corticosteroids (ICS) or anti-IgE therapy within 6 months prior to Screening Visit 1B/C.
- 5. Forced expiratory volume in 1 second (FEV1) <80% of predicted, or other evidence of partly controlled or uncontrolled asthma.
- 6. Clinically significant confounding symptoms of allergy to relevant local seasonal allergens (e.g. ragweed, mugwort, tree, grass or mould) and cannot complete the BAE and the final PAC period at 50-52 weeks (PAC3) outside the respective allergy seasons.
- 7. IgE ≥0.35 kU/l to other perennial allergens (e.g. animal dander, cockroach, mould) which cannot be avoided during the study or where sampling for these allergens demonstrates significant levels within the subject's home from dust and/or vacuum cleaner samples, analysed using Indoor Biotechnologies Allergen Analysis Service.

VERSION FINAL 4.0 CONFIDENTIAL PAGE 26 OF 92

- 8. Intends to be away for 7 days or more during the final PAC period at 50-52 weeks (PAC3), or whose lifestyle means that there is a high likelihood of them being away from home for more than 7 days during the PAC3 period.
- 9. Received an immunosuppressive treatment within 3 months prior to screening (except steroids for allergic and asthma symptoms).
- 10. Previous immunotherapy treatment with any HDM allergen for more than 1 month within 5 years prior to screening.
- 11. Receiving ongoing treatment with any specific immunotherapy at screening.
- 12. Administration of epinephrine is contraindicated (e.g. subjects with acute or chronic symptomatic coronary heart disease or severe hypertension).
- 13. Use of beta-blockers, alpha-adrenoceptor blockers or monoamine oxidase inhibitors within 14 days before the Screening Visit 1B/C.
- 14. History of significant recurrent acute sinusitis, defined as 2 episodes per year for the last 2 years, all of which required antibiotic treatment, or a history of chronic sinusitis, defined as sinus symptoms lasting greater than 12 weeks that include 2 or more major factors or 1 major factor and 2 minor factors. Major factors are defined as facial pain or pressure, nasal obstruction or blockage, nasal discharge or purulence or discoloured postnasal discharge, purulence in nasal cavity, or impaired or loss of smell. Minor factors are defined as headache, fever, halitosis, fatigue, dental pain, cough, and ear pain, pressure, or fullness.
- 15. Females who are pregnant, lactating or planning to become pregnant, or donate ova for *in vitro* fertilisation during the study period or within 30 days following the study period. Female subjects unwilling to employ appropriate contraceptive measures to ensure that pregnancy will not occur either during or for 30 days following the completion of study period.
- 16. Significant history of alcohol or drug abuse.
- 17. Previously been treated in this or another HDM-SPIRE (ToleroMune-HDM) study.
- 18. Any history of severe drug allergy, severe angioedema or anaphylactic reaction.
- 19. Received treatment with an investigational drug within 30 days prior to the study.
- 20. Are unable to communicate or to understand the requirements of the study, or exhibit any psychiatric disorder, which would impair communication between the subject and the Investigator thereby interfering with the informed consent procedure or the gathering of study data.

VERSION FINAL 4.0 CONFIDENTIAL PAGE 27 OF 92

- 21. History or findings on physical examination of any significant disease or disorder (e.g. cardiovascular, pulmonary, gastrointestinal, liver, renal, neurological, immunopathological, musculoskeletal, endocrine, metabolic, malignant, psychiatric, major physical impairment) which, in the opinion of the Investigator, may either put the subject at risk because of participation in the study, influence the results of the study or the subject's ability to participate in the study.
- 22. Dependent on the Investigator/site either for employment or education or are first degree relatives or partners of the Investigator/study staff.
- 23. Institutionalised because of a legal or regulatory order.
- 24. Active tuberculosis, auto-immune disorders, vaccination within 2 weeks before start of immunotherapy as well as subjects with hypersensitivity to excipients of HDM-SPIRE.

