Period 1, Consent, Screening and Baseline Allergy Evaluation: Rhinoconjunctivitis scores and allergy rescue medication usage will be collected. After consent has been obtained, screening will be conducted in a staged approach to minimise the number of investigations that a potentially ineligible subject undertakes. Firstly, a blood sample will be taken for measurement of IgE to Der f, Der p and relevant perennial allergens. This visit (visit 1A) may be performed during a seasonal allergen period and before the start of additional screening activities. Potential subjects with IgE above the required levels will complete, between visits 1A and visit 1B/C, a paper diary (pDiary) of symptoms for 1 week before additional screening activities are performed. Subjects found to be eligible based on these two steps will undergo screening up to a maximum of 8 weeks before randomisation which may consist of 1 or 2 visits to the clinic, at the Investigator's discretion. In exceptional circumstances, due to reasons beyond the control of the Investigator and/or subject (for example extreme weather), this 8 week period may be exceeded; however this requires documented approval by the Sponsor. Suitable subjects will record Baseline rhinoconjunctivitis symptom scores

VERSION FINAL 4.0 CONFIDENTIAL PAGE 21 OF 92

(RSS) using a 4-point categorical scale and RMS for a 3-week period in an eDiary before randomisation. The completion of the p Diary over 7 days, allergy screening and the BAE period will take place outside of any and all relevant seasonal allergy periods for each individual subject.

Period 2, Study Medication Administration: Subjects meeting the inclusion/exclusion criteria will be randomised to either one of the 3 active treatment groups or the placebo group in equal proportions.

A total of 8 doses of HDM-SPIRE or placebo will be administered, one dose every 4 weeks (±2 days), for a total duration of 28 weeks as shown in Table 2.

Table 2Dosing Schedule

Visit	3A	3B	3 C	3D	3E	3F	3G	3Н
Week (± 2 days)	0	4	8	12	16	20	24	28
Treatment Groups	Treatment Groups							
Placebo	P	P	P	P	P	P	P	P
HDM-SPIRE 4 x 12 nmol	X	X	X	X	P	P	P	P
HDM-SPIRE 4 x 12 nmol, two courses	X	X	X	X	X	X	X	X
HDM-SPIRE 4 x 20 nmol	X	X	X	X	P	P	P	P

X = Active doses; P = Placebo doses

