### Additional Exclusion Criteria at end of BAE

25. Used any oral or parenteral corticosteroid during the BAE period.

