## **5.8** Concomitant Medication and Dietary Supplements

### 5.8.1 Rescue Medication

Subjects may, at any time during the study, take allergy medication. During the BAE and PAC periods subjects will be asked to use only allergy rescue medication provided to the subject in the Rescue Medication Package according to the defined Rescue Medication Plan (Appendix 3).

The following allergy rescue medications will be provided to subjects and their use will be documented in their eDiaries during the BAE and PAC periods:

- Antihistamine eye drops
- Oral antihistamines
- Intranasal corticosteroids

If a subject finds that he or she is not able to obtain a comfortable level of relief from symptoms with the allergy rescue medications provided during the BAE, the Investigator and subject may agree to use alternative allergy rescue medications in the same categories as above. Alternative allergy rescue medications will be scored on the same RMS scale as the equivalent category of allergy rescue medication from the Rescue Medication Package. The Investigator may also prescribe oral corticosteroids, if required and their use will be documented in the subjects' eDiaries during the PAC periods.

A subject who uses any other category of allergy medications than those included in the Rescue Medication Package during the BAE Period will not be randomised. Use of any other category of allergy medications during the PAC periods will be considered a protocol deviation.

VERSION FINAL 4.0 CONFIDENTIAL PAGE 36 OF 92

Subjects will be instructed to record all allergy medications other than those provided in the Rescue Medication Package in the pDiary.

The recorded allergy rescue medication usage data in the eDiary will be transferred into the study database directly. No duplication of recording in eCRF is required.

All allergy rescue medications dispensed or prescribed to subjects as part of the Rescue Medication Package will be recorded in the eCRFs.

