## 6.2.1.2 Visits 2A and 2B: Baseline Allergy Evaluation

The Baseline Allergy Evaluation will take place during a 3-week period before randomisation and subjects will attend the clinic at the start and end of the BAE period, Visits 2A and 2B, respectively. The BAE must start after the end of the pollen period for all relevant seasonal allergens to which the subject has clinically significant symptoms and must complete at least 1 week before the anticipated start date of the Spring pollen season for any allergen to which the subject has clinically significant symptoms. The requirement to complete the BAE at least 1 week before the anticipated start date of the relevant Spring pollen season is intended to ensure the PAC3 period can also complete before the start date of the relevant Spring pollen season, 50-52 weeks after randomisation. This is illustrated schematically below.

For sites in the most Northerly latitudes with cold and dry winters the BAE should also generally take place before the onset of winter. Sites may be permitted to continue the BAE during winter months with the agreement of the Sponsor and where sampling of dust shows the presence of house dust mite allergen in the home at a suitable level.

Fall (Autumn) pollen season	Winter period - no relevant pollen in air	Spring/ Summer/ Fall (Autumn) pollen season	Winter period - no relevant pollen in air
Screening may occur	Baseline Allergy Evaluation occurs	PAC 1 and PAC 2 periods may occur during pollen periods	PAC3 period occurs
	Must complete at least 1 week before anticipated start date of relevant spring allergen to which subject has clinically significant symptoms		Must complete at least  1 week before anticipated start date of relevant spring allergen to which subject has clinically significant symptoms

VERSION FINAL4.0 CONFIDENTIAL PAGE 45 OF 92

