#### 6.2.1.2.1 Visit 2A

The following procedures will take place at Visit 2A:

- Each subject will be provided with an eDiary to record RSS, Asthma Symptom Scores (ASS) and allergy rescue medication use.
- Recording of any changes to concomitant medication since last visit.
- Recording of any AEs.
- Dispense a pDiary to record AEs and concomitant medications.
- Subjects will be requested to discontinue their current allergy medication. Subjects will be trained on how to follow the study-specific Rescue Medication (Appendix 3) and will be asked to only use medications from the Rescue Medication Package for the duration of the BAE.
- Dispense allergy rescue medication.

The following information will be recorded in the eDiary on a daily basis first thing in the morning for a period of 3 weeks:

- RSS on a 4 point categorical scale
- Allergy rescue medication use
- ASS

If a subject's allergic rhinoconjunctivitis symptoms become unacceptable to them, they may take allergy rescue medications from the Rescue Medication Package provided in accordance with the Rescue Medication Plan (Appendix 3). Subjects will be instructed to inform the Investigator if they have taken any allergy medication other than those prescribed from the Rescue Medication Package. The Investigator must record these allergy medications as concomitant medications in the eCRF.

For each symptom, the subject will rate the severity over the last 24 hours as follows:

- 0 = absent
- 1 = mild, barely noticeable
- 2 = moderate, annoying/troublesome
- 3 = severe, very annoying/ very troublesome

**RSS symptoms** will be captured as follows:

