# 6.2.2 Period 2: Study Medication Administration (Visits 3A-3H) and End of Dosing Assessment (Visit 3I)

## 6.2.2.1 Visits 3A-3H: Study Medication Administration

Subjects will be randomised when they attend Visit 3A [note: Visit 3A should immediately follow completion of Visit 2B, or if this is not convenient may occur within 7 days of Visit 2B]. Study medication, HDM-SPIRE or placebo, will be administered at 8 visits (Visits 3A-3H) for each subject (see also Section 3.1). The 8 visits will take place at intervals of 4 weeks (±2 days). If the subject has a significant systemic or local illness that includes a fever (oral or aural temperature >38°C), the dosing visit should be rescheduled for 5 days later; there is no need to reschedule dosing for subjects with an upper respiratory tract infection without any significant associated fever. If the subject's pre-dose FEV1 is <70% of predicted the dosing visit should be rescheduled. Subjects will be permitted to leave the clinic after a minimum of 30 minutes based on the Investigator's assessment of their clinical condition. Intradermal injections of HDM-SPIRE or placebo (100 µL) will be made into the flexor (volar) surface of the forearm by the Investigator or designee. Standards for practical allergen-specific immunotherapy are described in Alvarez-Cuesta et al (Alvarez-Cuesta 2006).

Emergency treatment must be available and immediately accessible for treatment of suspected anaphylactic reactions (see Section 5.8.2 and Appendix 2)

The following procedures and assessments will take place at each of the study medication administration visits (Visits 3A-3H):

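### The two systemic-corticosteroid exclusions do not meet: up to 35 days before randomisation fall under neither, so the baseline diary can carry steroid effect that the Combined Score does not count

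*Protocol*

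**What the plan says.** Two eligibility criteria deal with systemic corticosteroids. Both are in Protocol 4.3, and both are repeated in the synopsis.

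- Criterion 3: "Used any oral or parenteral corticosteroids at any time within 1 month prior to Screening Visit 1B/C".
- Criterion 25, applied at the end of the BAE: "Used any oral or parenteral corticosteroid during the BAE period".

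The timing comes from four other places.

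- Protocol 3.1 says that eligible subjects "will undergo screening up to a maximum of 8 weeks before randomisation". In exceptional circumstances "this 8 week period may be exceeded; however this requires documented approval by the Sponsor". Table 5 shows the same 8-week maximum.
- Protocol 6.2.1.2: "The Baseline Allergy Evaluation will take place during a 3-week period before randomisation", running from Visit 2A to Visit 2B.
- Protocol 6.2.2.1 places randomisation at Visit 3A and notes that "Visit 3A should immediately follow completion of Visit 2B, or if this is not convenient may occur within 7 days of Visit 2B".
- SAP 3.1 takes as BAE scores all diary entries dated from Visit 2A up to and including Visit 2B.

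On medication between screening and the diary, Protocol 5.8.1 states: "Subjects may, at any time during the study, take allergy medication". At Visit 2A, Protocol 6.2.1.2.1 adds: "Subjects will be requested to discontinue their current allergy medication".

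**The concern.** Criterion 3 stops at Visit 1B/C and criterion 25 starts at Visit 2A. Nothing requires the two visits to be close together. Systemic corticosteroid used in between breaches neither criterion, even on the day before the diary starts.

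The diary that follows has four uses:

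- the entry check of mean TRSS at least 12 (Protocol 4.2, criterion 9);
- the randomisation stratum, TRSS below 16 or at least 16 (Protocol 5.7);
- the baseline CS covariate, also crossed with period, in the primary mixed model (SAP 15.1.3);
- the reference value for percentage reduction in the responder analysis (SAP 15.1.5.1).

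CS adds a rescue-medication score to the symptom score so that symptom relief obtained with medication is counted. RMS scores only medication used on a diary day. If a course or depot injection given before the diary still suppresses symptoms, TRSS falls and RMS stays at 0. Baseline CS then understates that subject's disease. Criterion 25 speaks of use during the BAE and does not say whether residual effect of an earlier injection counts.

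**Working it through.** The documents give no figure for the uncovered interval, so there is none to reproduce. It follows from the visit schedule.

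**Step 1. Length of the gap.** Inputs: at most 8 weeks = 56 days from screening to randomisation (Protocol 3.1, Table 5); BAE of 3 weeks = 21 days (6.2.1.2); 0 to 7 days from Visit 2B to Visit 3A (6.2.2.1).

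Uncovered days before the BAE = 56 - 21 - (delay from 2B to 3A).

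- Delay 0: 56 - 21 - 0 = 35 days before the BAE and 0 after it, total 35.
- Delay 7: 56 - 21 - 7 = 28 days before the BAE and 7 after it, total 35.

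With no delay, screening 3, 4, 5, 6, 7 or 8 weeks before randomisation gives a gap of 0, 1, 2, 3, 4 or 5 weeks. Thirty-five days is the ordinary maximum, not a typical value. Only a Sponsor-approved extension takes it higher.

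**Step 2. Does another rule close it?**

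- Protocol 5.8.1 withholds randomisation for other categories of allergy medication only when they are used during the BAE.
- Protocol 5.8.5 bars beta-blockers, alpha-adrenoceptor blockers and monoamine oxidase inhibitors in Periods 1 and 2. Corticosteroids are not on that list.
- Criterion 9 on immunosuppressants looks back from screening and exempts steroids given for allergic or asthma symptoms.
- Visit 2A stops current allergy medication from that day, with no interval before it.
- The Visit 2B re-check (6.2.1.2.2) repeats the exclusion criteria, but criterion 3 stays tied to Visit 1B/C.
- Criteria 2, 5 and 21 may remove some of these subjects for asthma deterioration, poor asthma control or other disease. None of them concerns steroid use as such.

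The three drug classes in 5.8.5 make a useful contrast. Criterion 13 looks back from Visit 1B/C and 5.8.5 continues the bar through Periods 1 and 2, so those windows join. The corticosteroid windows do not.

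**Step 3. Scale.** The frequency of use in the gap and the size of any carry-over are not in the documents, so the following is assumed. Suppose carry-over lowers a subject's mean BAE TRSS by 4 points over the whole diary. Baseline CS falls by 4/8 = 0.5. If a fraction p of subjects is affected, the added baseline variance is p(1 - p) x 0.5^2.

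- p = 2%: 0.02 x 0.98 x 0.25 = 0.0049.
- p = 5%: 0.05 x 0.95 x 0.25 = 0.0119.

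The baseline SD is not stated. With the planning SD as a stand-in, 0.986^2 = 0.972, so the addition is 0.5% to 1.2%. The plan's calculation (difference 0.32, SD 0.986, two-sided 5%, 80% power) reproduces as 150 per group. Required size is proportional to variance. Even if all the added variance reached the residual, 150 would rise by 150 x 0.0050 = 0.8 to 150 x 0.0122 = 1.8 subjects per group.

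**The case against.** The best case against the point is that it hardly matters. Exposure in the gap before Visit 2A precedes randomisation, so it is balanced between arms in expectation. The TRSS threshold of 12 turns away strongly suppressed subjects. Allergy medication of any class is allowed until Visit 2A, so the protocol already accepts some carry-over. All of this stands, and it limits the size of the point. It does not close the gap: systemic corticosteroid is the class for which the sponsor wrote two dedicated exclusions, and they leave an interval between them.

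A reader might infer more than the documents support:

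- *That the exposed time is 35 + 7 = 42 days.* The 8-week limit runs to randomisation at Visit 3A, so any delay after Visit 2B comes out of the same 56 days. Steroid taken after Visit 2B also cannot change BAE scores.
- *That an affected subject looks like a non-responder in any arm.* Suppose TRSS is suppressed to 14 with RMS 0. Baseline CS is 14/8 = 1.75. At the planned active mean of 1.28 the reduction is (1.75 - 1.28)/1.75 = 27%, above the 20% level in Protocol 7.5.3.1.2. The apparent response is attenuated, not removed.
- *That a 0.5 baseline shift outweighs the planned difference of 0.32.* The first is an assumed change in one subject; the second is a difference between group means.
- *That a wrong stratum distorts the primary comparison.* The model in SAP 15.1.3 uses continuous baseline CS and has no TRSS stratum term. The SAP uses the category only for disposition and baseline summaries (sections 9 and 10).
- *That the sponsor set a steroid-free month before symptom diaries.* Criterion 3 counts back from Visit 1B/C, and the screening diary occupies the 7 days before that visit. No passage states such a standard for diaries.

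**Conclusion.** The point holds as a gap in eligibility wording. Following the plan exactly, up to 35 days in total are covered by neither corticosteroid exclusion, or more with Sponsor approval, and use up to the day before the baseline diary leaves a subject eligible. That conclusion rests on the text alone.

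The consequence is noise in the four uses of the BAE diary. How much cannot be computed from the documents. Under the assumed 2% to 5% of subjects and a 0.5 shift in CS, it is worth fewer than 2 subjects per group, so the effect on precision is probably small. No bias between arms is expected. This is a cheap improvement to baseline quality, not a threat to the primary comparison.

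**What to change.** In Protocol 4.3 and in the synopsis, reword criterion 25 so that the exclusion for oral or parenteral corticosteroid use runs from Visit 1B/C through the end of the BAE at Visit 2B. Leave criterion 3 as it is. The two existing windows then join, and no new washout length is introduced. The exclusion need not reach Visit 3A for this purpose, because the baseline scores are complete at Visit 2B.

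The check uses the concomitant-medication record already made at Visits 2A and 2B, so no assessment is added. The cost is one eligibility sentence in two places, and a few subjects who use systemic corticosteroid in that interval would not be randomised.
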